#### Cost-effectiveness and cost-utility analysis

For these analyses we will use SPSS statistical software and Excel (for the Bootstraps). Respondents for whom at least 75% of the data per measurement instrument are available will be included in the analysis. Missing cost and outcome data will be imputed using multiple imputation (MI) methods and last-observation carried forward (LOCF), for intention to treat (ITT) analysis following Dutch guidelines (Zorginstituut Nederland 2016).

A baseline analysis will be performed to examine the comparability of groups at baseline for both costs and outcomes. If necessary methods will be applied to control for differences in baseline (Manca, Hawkins, & Sculpher, 2005). To investigate whether data are normally distributed a Kolmogorov-Smirnov test will be performed. Despite the usual skewness in the distribution of costs, the arithmetic means will be generally considered the most appropriate measures to describe cost data (Barber & Thompson, 2000; Ramsey et al., 2005). Therefore arithmetic means (and standard deviations) will be presented. In case of skewness of the cost data, non-parametric bootstrapping will be used to test for statistical differences in costs between the intervention and control group. Non-parametric bootstrapping is a method based on random sampling with replacement based on individual data of the participants (A. H. Briggs, Wonderling, & Mooney, 1997). The bootstrap replications will be used to calculate 95% confidence intervals around the costs (95% CI), based on the 2.5th and 97.5th percentiles. If cost data are distributed normally, t-tests will be used.

The Incremental cost-effectiveness ratio (ICER) will be determined on the basis of incremental costs and effects of MBCT compared to TAU. The cost-effectiveness ratio will be stated in terms of costs per outcome rate (IDS-C), the cost-utility ratio will focus on the cost per QALY gained.

The ICER will be calculated as follows. ICER = (Ci - Cc) / (Ei - Ec), where Ci is the total cost of the MCBT group, Cc is the total cost of the TAU group, Ei is the effect at 12 months follow-up for the MCBT group and Ec is the effect at 12 months follow-up for the TAU group.

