## 2. OBJECTIVES

Primary Objective:

• Is MBCT as an adjunctive treatment to TAU more effective in reducing depressive symptoms in patients with bipolar disorder, compared to TAU alone?

Secondary Objective(s):

- Is MBCT more effective than TAU in reducing levels of (hypo)manic and anxiety symptoms, the risk of relapse in depression or (hypo)mania, and ruminative brooding?
- Is MBCT equally effective in patients with < 12 mood episodes compared to patients with =/> 12 episodes?
- Is MBCT more effective than TAU in improving mindfulness, self-compassion, functioning, and mental health/well-being?
- From the viewpoint of the society, is adding MBCT to TAU preferable in terms of societal costs and QALYs, compared to TAU alone?

Our hypothesis is that participants allocated to MBCT will have fewer depressive, (hypo)manic, and anxiety symptoms and experience fewer (hypo)manic or depressive episodes than those allocated to TAU over the 15 months study period. In addition, we hypothesize that MBCT will be associated with improvement in several areas of functioning and well-being. Furthermore, we expect that positive outcomes will be (partially) mediated by a reduction of ruminative thinking, and improvement of mindfulness and self-compassion skills.

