## 4.4 Sample size calculation

Sample size calculation is based on the estimated change in depressive symptoms form pre- to posttreatment. As we aim to include patients with all levels of depressive symptoms, we based our calculation on a previous study conducted at the Radboudumc Centre for Mindfulness (van Aalderen et al., 2012). In this study, levels of depression as assessed with the Inventory of depressive symptomatology – self-rated (IDS-SR) decreased in the MBCT+TAU group (n = 102) from 14.9 ( $\pm$  9.2) to 10.3 ( $\pm$  7.8) whereas the TAU group (n = 103) showed no change in depression levels (pretreatment: M = 16.2 ( $\pm$  9.4) and posttreatment: M = 16.2 ( $\pm$  9.8). This corresponded to an effect size of 0.5 for reduction of depressive symptoms in patients with recurrent (unipolar) depression (remitted n = 124, currently depressed n = 58). Based on a two-sided test with an alpha of 0.05 and a power of 80%, with an estimated effect size of 0.5, including a design factor of 1 – r2 (0.75), and taking account of a conservative estimate of 40% loss to follow-up, we intend to recruit N = 160 patients (80 per group).

We anticipate that about 25% of the population will have to be excluded due to (hypo)manic symptoms (when exceeding the maximum on the Young Mania Rating Scale) or other exclusion criteria. We further expect about 25% of the eligible patients to be interested in the study.

Approximately 690 BD patients are treated in ProPersona, with 518 (75%) meeting the inclusion criteria, of whom 130 (25%) would probably be interested to participate. The intended number of participants (n = 60) falls comfortably within this estimate. The number of BD patients treated in Dimence is about 900, with 675 (75%) meeting the inclusion criteria, of whom 169 (25%) would probably be interested to participate. Again, the intended number of participants (n = 50) falls well within this estimate. Approximately 650 BD patient are treated in Altrecht, with 100-150 new patients per year. About 487 (75%) of BD patients would be meeting the inclusion criteria, of whom 122 (25%) would probably be interested. The intended number of participants (n = 50) therefore seems feasible. Moreover, we will recruit patients through the patient association Vereniging voor Manisch Depressieven en Betrokkenen (VMDB) and the psychiatry department of the Canisius Wilhelmina

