## 6.3 Study procedures

Figure 2 provides a flowchart of the study procedures from referral to the final assessment. Patients will be recruited from several specialized, outpatient clinics in the Netherlands; ProPersona, Dimence, and Altrecht, and through the patient association; Vereniging voor Manisch Depressieven en Betrokkenen (VMDB). They will receive a letter from their attending clinicans, informing them about the study with an included information leaflet. This way, patients are free to choose whether to participate in the study, without feeling obligated to their clinicans when asked face-to-face. Interested patients are, after verbal consent is obtained, invited for a screening by telephone to assess global eligibility. Eligible patients will receive more information and a detailed description of the study procedure. After one week, patients will be contacted by telephone to assess whether they are still interested in participation. Patients who are still interested to participate will be invited for intake with a research assistant, where informed consent is obtained. They are thoroughly screened for in- and exclusion criteria with use of the SCID-I and YMRS. Altogether, this will take about 1.5 hours. When patients are still eligible and interested, they are invited for baseline assessment (T0), which consists of several clinician administered measures (IDS-C and FAST), which will take about 20 minutes. After a short pause, participants are asked to conduct five short computer tasks (Stroop, Emotional Stroop Task, Breathing Focus Task, Self Referent Encoding Task, and Attentional Control Scale). This will take about onee hour. However, it is possible for participants to do only the first part of these measures, so they can skip the computer tasks if necessary. Furthermore, participants are asked to fill in several self-report questionnaires at home (STAI, brooding subcale of RRS, CHIME, SCS-SF, MHC-SF, RPA, CTQ, TiC-P, and EQ-5D-5L). After baseline assessment, patients are randomised to one of two groups: TAU or MBCT + TAU. Participants in the intervention group (MBCT + TAU) will receive an eight-week MBCT training, during which they daily have to document mood fluctuations, changes in medication, and major life events in the Life Chart. Furthermore, participants are asked to document adherence and adverse events in a personal diary. Participants in the comparator group (TAU) will receive their treatment as usual, while they daily document in the Life Chart as well. After three months (T1), participants are invited for follow-up assessment, during which the clinician administered questionnaires (YMRS, IDS-C, FAST, SCID-I) and computer tasks will be conducted again. Furthermore, patients are asked to fill out the online self-report questionnaires a second time. More follow-up assessments will take place after 6 months (T2), 9 months (T3), 12 months (T4), and 15 months (T5). During T2, T3, and T4 assessments patients are approached by telephone to assess depressive, manic, and anxiety symptoms, and global functioning over the past three months (IDS-C, YMRS, FAST, and SCID-I to assess manic and depressive symptoms retrospectively). Furthermore, during these assessments patients are asked to fill out the online questionnaires as well. The assessment at 15 months follow-up (T5), will consist of the clinician adminstered meassurements (IDS-C, YMRS, FAST) and the online self-report measurements (STAI, brooding subcale of RRS, CHIME, SCS-SF, MHC-SF, RPA, TiC-P, EQ-5D-5L). Table 1 provides an overview of the assessments. After 15 months of follow-up the study will end, after which participants in the comparator group will be given the opportunity to participate in a MBCT-course as well.

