# 8. STATISTICAL ANALYSIS

Multilevel analysis will be used to account for the cluster-randomized design and therefore the hierarchical structure of the data, with outcome variables at the pre- and postmeasurements at the lowest level, nested within individuals, nested within treatment groups (for the intervention condition), and nested within condition (MCBT + TAU vs TAU). Any baseline parameters that may be inadvertently unequally distributed between the conditions are included as covariates. Multilevel logistic regression will be performed for dichotomous outcomes and multilevel regression analysis for normally distributed continuous outcomes. The clinical outcome data will be analysed and reported according to the CONSORT guidelines, i.e. on intention-to-treat basis. Given the anticipated drop-out, we will also analyze and report on the per-protocol group, and discuss possible differences between the two analysis sets.

Additional analyses will be performed within subgroups with and without a current depressive episode. To account for possible differences between therapy groups, we will add a random group effect. Sensitivity analyses will be conducted with different scenarios of imputed data sets, in case of missing data, to examine the influence of missing data on the pattern of outcomes.

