## Sensitivity analysis

Stochastic uncertainty of the ICER will be handled using 2,500 non-parametric bootstraps and by plotting the simulated ICERs on the ICER plane. Bootstrap simulations will be conducted in order to quantify the uncertainty around the ICER, yielding information about the joint distribution of cost and effect differences. The bootstrapped cost-effectiveness ratios will be subsequently plotted in a cost-effectiveness plane, in which the vertical line reflects the difference in costs and the horizontal line reflects the difference in effectiveness. The choice of treatment depends on the maximum amount of money that society is prepared to pay for a gain in effectiveness, which is called the willingness-to-pay (WTP) ceiling ratio. For decision-making purposes, the ICER acceptability curve will be plotted for various WTP) ceilings for making judgments whether discontinuation offers good value for money relative to routine medical care. Deterministic one-way sensitivity analyses directed at uncertainty in the main effects and main cost drivers will be performed to assess the robustness of our findings. Additionally, a multi-way sensitivity (scenario-) analyses will recalculated in order to assess whether the assumptions have influenced the incremental cost-effectiveness ratio (ICER), for example by varying cost-prices and volumes between minimum and maximum (A. H. Briggs et al., 1997).

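### Read literally, the 75% completeness rule in Protocol section 8.2 removes randomised patients before imputation from an economic analysis labelled intention-to-treat

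*Protocol*

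**What the plan says.** Under Cost-effectiveness and cost-utility analysis in Protocol section 8.2, the entry rule is: "Respondents for whom at least 75% of the data per measurement instrument are available will be included in the analysis". The next sentence says that missing cost and outcome data will be "imputed using multiple imputation (MI) methods and last-observation carried forward (LOCF), for intention to treat (ITT) analysis", and refers to Dutch guidelines. The same subsection takes the IDS-C as the effect in the cost-effectiveness ratio and the QALY as the effect in the cost-utility ratio.

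For the clinical outcomes, the opening of section 8 says: "The clinical outcome data will be analysed and reported according to the CONSORT guidelines, i.e. on intention-to-treat basis". It sets no completeness threshold. It also promises sensitivity analyses under several imputation scenarios if data are missing.

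Under Sensitivity analysis in section 8.2, "Stochastic uncertainty of the ICER will be handled using 2,500 non-parametric bootstraps". Scenario analyses of the assumptions are added, with the example of doing so "by varying cost-prices and volumes between minimum and maximum".

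The economic question is a stated secondary objective in section 2: "is adding MBCT to TAU preferable in terms of societal costs and QALYs". Section 4.4 sets N = 160, "taking account of a conservative estimate of 40% loss to follow-up".

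**The concern.** The rule has people as its subject and admission to the analysis as its action, and it depends on something observed after randomisation. An intention-to-treat analysis keeps everyone randomised and imputes what is missing. If incomplete patients are removed first, imputation only fills gaps among those who remain, and the label no longer describes the set.

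Two things follow. First, incompleteness may be related to costs or to effects, and differently so in the two arms, in which case both parts of the ICER can be biased. Second, the IDS-C could be estimated in one set for the clinical report and in another for the ICER.

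The sets can part even for patients who never drop out. At T2 to T4 the IDS-C is taken by telephone, whereas for self-report section 6.3 says that "during these assessments patients are asked to fill out the online questionnaires as well". Table 1 lists the TiC-P and EQ-5D-5L at those visits. If failing one instrument removes the patient, someone with every IDS-C interview could be excluded on the TiC-P alone.

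**Working it through.** **1. The plan's own figure.** Inputs from section 4.4: two-sided alpha 0.05, power 80%, effect size 0.5, design factor 0.75, loss 40%.
- n per arm = 2 × (1.960 + 0.842)² / 0.5² = 62.8, so 63.
- 63 × 0.75 = 47.25, so 48.
- 48 / (1 − 0.40) = 80 per arm, 160 in total.

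This reproduces N = 160. The sample size is not in dispute.

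**2. The sentences in order.** Sentence one admits respondents by completeness. Sentence two imputes and names the result intention-to-treat. Neither says that randomised patients below 75% are kept and imputed, and no other section says so.

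**3. What 75% could count.** The text does not say whether the unit is items or assessments. Take a patient complete at T0, T1 and T2 and then lost:

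| Unit counted | Needed for 75% | This patient | Result |
|---|---|---|---|
| Assessments T0–T4 (to 12 months) | 0.75 × 5 = 3.75, so 4 of 5 | 3 of 5 = 60% | out |
| Assessments T0–T5 | 0.75 × 6 = 4.5, so 5 of 6 | 3 of 6 = 50% | out |
| Items within one TiC-P (38 items) | 0.75 × 38 = 28.5, so 29 of 38 | three questionnaires complete | can stay in, later ones imputed |

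Two analysts could follow the same paragraph and analyse different patients.

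**4. Illustrative set sizes.** Only the 40% loss is the protocol's figure. The other shares are assumptions.
- Exactly the lost patients fail: 160 × 0.60 = 96 remain, 64 fewer.
- A further 10% or 20% of those still in follow-up also fail: 96 × 0.90 = 86.4, or 96 × 0.80 = 76.8.
- 25% or 50% of the 64 lost still pass: 96 + 16 = 112, or 96 + 32 = 128.
- Item-scoring reading with imputation below the threshold: 160 remain.

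So 96 is neither a bound nor a forecast.

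**5. Bias.** In one arm let p be the share excluded and d the mean of the excluded minus the mean of the included. Then the mean of the included minus the mean of all randomised is −p × d. For the arm difference (I = MBCT + TAU, C = TAU), before any baseline adjustment, the bias is −pI × dI + pC × dC. It is zero if both d are zero or if the two products are equal, and otherwise it can take either sign. The protocol gives neither p nor d, so no value can be derived.

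**6. Whether a planned analysis would expose this.** Bootstrapping resamples the patients already admitted. The imputation scenarios in section 8 are described as varying imputed data, and the scenario analyses in section 8.2 as testing assumptions. Neither is stated to bring back patients whom the 75% rule removed.

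**The case against.** The strongest reply is that the literal reading makes the imputation sentence nearly pointless, while another reading gives both sentences work to do. An instrument with at least 75% of its data is used, and anything below is treated as missing and imputed. The reference to each measurement instrument fits that, and respondents may simply mean people who returned a questionnaire. Admission could also be meant instrument by instrument, so that failing the TiC-P would not remove a patient's IDS-C. These readings are plausible, and the TiC-P example above holds only if one failure removes the patient altogether. But the protocol states none of them, and its words select people for the analysis.

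It can also be said that an analysis plan not shown here may settle this. That would answer a missing detail. Here the protocol states a rule and then attaches a label that the rule, as worded, contradicts.

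Other safeguards deserve weight. The section 8 imputation scenarios are not limited to clinical outcomes. Prices and volumes are only an example of the section 8.2 scenarios, so varying the analysis set is not ruled out. Section 6.6 has dropouts telephoned for their remaining questionnaires, which may reduce the number who fail. Section 8.2 allows adjustment for baseline differences. Each of these may lessen the problem, but none is stated to restore an excluded patient.

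A reader might infer that 64 patients will be lost, or might express a bias as a share of the 0.5 effect size. The documents support neither. The 64 requires all of the lost patients, and only those, to fail, and the protocol calls its 40% conservative. The 0.5 is a pre-to-post, self-rated effect in unipolar depression and is no yardstick for 12-month costs or QALYs.

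**Conclusion.** The point holds in limited form. As worded, section 8.2 can screen out randomised patients on post-randomisation completeness and still call the result intention-to-treat, and nothing elsewhere in the protocol reconciles the two. It rests on reading the entry rule literally. Under the item-scoring reading with imputation no one is removed, and only the wording needs repair.

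The size and direction of any bias are unknown, and it may be zero. The figure of 96 of 160 is an illustration under one assumption about who fails. It would go too far to conclude that the economic result will be biased, or biased towards one arm. The consequence is confined to the secondary economic evaluation. The primary endpoint and N = 160 stand. The choice of LOCF is not at issue here.

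**What to change.** In section 8.2, state that the base-case cost-effectiveness and cost-utility analysis includes all randomised patients, with missing cost and outcome data multiply imputed. Then give the 75% rule one of two defined roles:

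- a scoring rule for a single questionnaire, where a questionnaire below the threshold is treated as missing and imputed, and no randomised patient is removed; or
- the definition of a labelled sensitivity set, stating whether items or assessments are counted.

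This needs only a few sentences and no new data. The cost is slightly more imputation work and possibly wider intervals.

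### The economic analysis imputes missing costs and outcomes by both multiple imputation and LOCF with no stated base case, and LOCF is a poor assumption in a relapsing illness

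*Protocol*

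**What the plan says.** The part of Protocol section 8.2 on cost-effectiveness and cost-utility says that gaps in costs and outcomes are "imputed using multiple imputation (MI) methods and last-observation carried forward (LOCF", and labels the result intention-to-treat. The two methods stand side by side. Nothing says which one produces the reported result, or which gaps each one fills.

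The sentence just before sets an inclusion rule: "Respondents for whom at least 75% of the data per measurement instrument are available will be included in the analysis". It does not say whether this means items within one visit or data across visits.

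The ICER takes its effect at one year ("Ei is the effect at 12 months follow-up for the MCBT group"). On the measures it says: "The cost-effectiveness ratio will be stated in terms of costs per outcome rate (IDS-C), the cost-utility ratio will focus on the cost per QALY gained".

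For sensitivity analysis, 8.2 plans 2,500 bootstraps, one-way analyses of main effects and cost drivers, and scenario analyses with prices and volumes as examples. The imputation method is not listed. The opening of section 8 separately plans imputation scenarios for missing data, without mentioning LOCF. Section 6.6 has dropouts telephoned and asked for the remaining questionnaires, which they may refuse.

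On the expected amount of missing data, section 4.4 sizes the trial by "taking account of a conservative estimate of 40% loss to follow-up".

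**The concern.** LOCF assumes that IDS-C, EQ-5D-5L and resource use stay where they were at the last contact. The protocol's own account of the illness argues against this. Section 1 describes recurrent episodes, symptoms about half of the time, and relapse in 60% of patients within two years. Section 7.2.2 cites an earlier bipolar MBCT trial with median times to depressive relapse of 53 and 46 days. Carrying one TiC-P assessment forward repeats an admission, or its absence, at every later assessment.

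LOCF is also a single imputation. The bootstrap resamples filled-in values as if they had been measured, so the cost and ICER intervals and the acceptability curve understate the uncertainty.

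Three things are at stake. The ratio can be biased in either direction. MI and LOCF can give two different ICERs, with nothing fixed in advance about which one leads. And the IDS-C effect in the cost-effectiveness ratio could differ from the IDS-C effect in the clinical analysis, which uses a repeated-measures model without LOCF. Trial costs also feed the budget-impact analysis.

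**Working it through.** **1. Is 40% loss really the protocol's planning figure?** Section 4.4 gives: "Based on a two-sided test with an alpha of 0.05 and a power of 80%, with an estimated effect size of 0.5", a design factor of 0.75, and 40% loss.

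- Per arm, unadjusted: 2 × ((1.96 + 0.84)/0.5)² = 62.8, so 63.
- With the design factor: 62.8 × 0.75 = 47.1, so 48. The t-based 64 × 0.75 is also 48.
- With loss: 48/(1 − 0.40) = 80 per arm, so 160 in total.

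The stated 160 is reproduced, so loss of up to 40% is a scenario the trial plans for. The protocol calls that figure conservative.

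**2. What LOCF does to the effect difference.** Section 4.4 gives the planning changes: MBCT + TAU from 14.9 to 10.3, a change of −4.6; TAU from 16.2 to 16.2, a change of 0. Let d_M and d_T be the fractions lost straight after T0, and Δ_M and Δ_T the changes that each arm would have shown. A carried-forward T0 value contributes a change of zero, so

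LOCF difference = (1 − d_M) × Δ_M − (1 − d_T) × Δ_T.

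With equal loss d and Δ_T = 0 this is (1 − d) × (−4.6). At a fixed cost difference the ICER is multiplied by 1/(1 − d).

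| Loss d | LOCF difference (points) | ICER factor |
|---|---|---|
| 10% | −4.14 | 1.11 |
| 20% | −3.68 | 1.25 |
| 30% | −3.22 | 1.43 |
| 40% | −2.76 | 1.67 |

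**3. Unequal loss, and change under TAU.** Here the true difference is kept at −4.6, and TAU changes of ±2 points are assumed.

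- 40% MBCT and 20% TAU loss, TAU improves by 2: 0.6 × (−6.6) − 0.8 × (−2) = −2.36.
- Same loss, TAU worsens by 2: 0.6 × (−2.6) − 0.8 × 2 = −3.16.
- 10% MBCT and 40% TAU loss, TAU improves by 2: 0.9 × (−6.6) − 0.6 × (−2) = −4.74, which is larger than the true 4.6.

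So the effect is usually shrunk in these examples, but it can also be exaggerated. Patients who leave later carry a T1 to T3 value instead. If a benefit seen at T1 fades by 12 months, carrying it forward flatters the arm.

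**4. When there is no mean bias.** If leavers truly remain at their baseline level, their true change is zero. LOCF from T0 then gives the right mean, although it still understates uncertainty.

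**5. What cannot be computed.** The protocol gives no cost or utility figures, so the effect of LOCF on the cost difference and on QALYs cannot be sized.

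**6. The 75% rule.** If it is read within a visit, leavers stay in the analysis and their later visits are imputed. If it is read across visits, early leavers are excluded, which contradicts the intention-to-treat label in the next sentence. Either way the text needs clarifying.

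**The case against.** A reader might infer that everyone who leaves is filled in by LOCF, is frozen at pre-treatment values, and thereby inflates the ICER 1.67-fold. The protocol does not support that.

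- MI is named first, and nothing makes LOCF the sole or base-case method.
- Only patients with no data after T0 would carry pre-treatment values, and the 75% rule, if read across visits, would exclude them.
- Section 6.6 seeks the remaining questionnaires from dropouts, and the TiC-P and EQ-5D-5L are self-report questionnaires.
- The 1.67 factor takes the full 40% as lost straight after T0 and assumes that leavers would otherwise have gained all 4.6 points. It holds costs fixed, although LOCF alters costs too. It also applies a pre-to-post IDS-SR change from unipolar patients to a 12-month IDS-C effect.

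All of this stands, and it is why the figures are an illustration and not an estimate.

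It can also be said that the choice of primary method belongs in an analysis plan not shown here, and that the planned scenario analyses leave room to show both results. This stands only in part. The protocol has already prescribed LOCF next to MI for the intention-to-treat analysis. That is a stated choice of method, and no passage labels it a sensitivity analysis. It would be speculation to say that the more favourable ICER will be picked later; the text merely leaves that open.

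**Conclusion.** The point holds in this form: section 8.2 prescribes MI and LOCF together for missing costs and outcomes, with no base case. LOCF is implausible in a recurrent illness and makes the intervals and acceptability curve too narrow.

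The direction of bias is not fixed. The shrinkage from 4.6 to between 4.14 and 2.76 points (ICER factor 1.11 to 1.67) is an upper illustration for equal loss of 10% to 40%. It rests on LOCF alone, loss straight after T0, leavers otherwise following their arm's mean, and a fixed cost difference. Unequal loss can move the figure further or reverse it.

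Only the economic evaluation and what draws on it are touched. The primary IDS-C analysis in section 8.1 uses a repeated-measures multilevel model without LOCF, and the sample size is unaffected. The change should be made before results are known, but the trial's main question does not depend on it.

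**What to change.** In section 8.2:

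- Make MI the single base case for missing costs, EQ-5D-5L and IDS-C, done separately by arm and using baseline and all observed follow-up values.
- Delete LOCF, or keep it only as a labelled sensitivity analysis.
- Examine departures from the MI assumption with MI-based scenarios, for example worse utility or higher costs after withdrawal, in line with the imputation scenarios already planned at the opening of section 8.
- State whether the 75% rule applies to items within a visit or across visits, and word it so that it does not exclude randomised patients from an analysis labelled intention-to-treat.

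The cost is a few sentences and slightly more analysis work. No new data are needed.

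### Baseline adjustment of the QALY and cost comparison is left to an undefined judgement after seeing baseline; it should be fixed in advance

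*Protocol*

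**What the plan says.** The part of protocol section 8.2 on cost-effectiveness and cost-utility first plans an analysis of how comparable the arms are at baseline, for both costs and outcomes. It then says: "If necessary methods will be applied to control for differences in baseline", citing a methods paper on controlling for baseline utility. It does not say what would make adjustment necessary, or which model would be used.

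The cost test that it does specify is unadjusted: non-parametric bootstrapping if costs are skewed, otherwise "If cost data are distributed normally, t-tests will be used". The ICER is the difference in total cost divided by the difference in effect at 12 months. It is bootstrapped 2,500 times for the cost-effectiveness plane, and an acceptability curve follows.

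The baseline data exist. Section 6.3 lists "CHIME, SCS-SF, MHC-SF, RPA, CTQ, TiC-P, and EQ-5D-5L" among the T0 questionnaires, and Table 1 marks both economic instruments at T0 and at T1 to T5. The text of section 6.3 places T0 before allocation: "After baseline assessment, patients are randomised to one of two groups".

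Section 8 has a general covariate rule for the clinical multilevel models. It too depends on observed imbalance, so it would not make economic adjustment unconditional even if it were read to apply here.

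**The concern.** Cost per QALY answers a stated secondary objective (section 2). If the QALY is the area under the utility curve from T0, the baseline utility is itself part of the outcome. A chance difference between arms at T0 then enters the QALY difference, whether or not a comparability check flags it. Baseline cost plays a similar but usually weaker role for total cost.

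A rule that looks first and adjusts afterwards has two drawbacks. It keeps imbalances that seem too small to act on, and it leaves the choice of estimator open until data have been seen. Both carry through to the ICER, the plane and the acceptability curve. The protocol's own sample size already counts on a gain from baseline adjustment for the primary outcome, so the principle is accepted elsewhere in the document.

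**Working it through.** **1. The plan's own figure.** Section 4.4 assumes a two-sided 5% test, 80% power and a standardised difference of 0.5. For the baseline correlation it reports "including a design factor of 1 – r2 (0.75"). It then allows for 40% attrition and arrives at this target: "we intend to recruit N = 160 patients (80 per group").

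- Unadjusted n per arm: 2 × (1.96 + 0.8416)² / 0.5² = 62.8.
- Times 0.75: 47.1, rounded up to 48 evaluable.
- Divided by 0.60: 80 per arm, 160 in total. The figure reproduces.

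The factor 0.75 implies r = 0.5, but for a depression score. No correlation is given for utility or cost, and no precision target for the economic analysis.

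**2. Assumptions.** 12-month trapezoid QALY from T0 to T4 with weights 0.125, 0.25, 0.25, 0.25, 0.125; 48 per arm; between-visit correlation ρ of 0.3, 0.5 or 0.7, either equal across visits or decaying as ρ to the power of the number of visits apart.

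**3. Share of QALY variance explained by baseline (R²), in units of utility SD.**

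- Equal correlation: variance = ρ + (1 − ρ) × 0.21875; covariance with baseline = 0.125 + 0.875ρ. At ρ = 0.5 these are 0.609 and 0.5625, so R² = 0.5625² / 0.609 = 0.52.
- Decay at ρ = 0.5: covariance = 0.125 + 0.25 × (0.5 + 0.25 + 0.125) + 0.125 × 0.0625 = 0.352. Variance = 0.21875 + 2 × (0.1875 × 0.5 + 0.125 × 0.25 + 0.0625 × 0.125 + 0.015625 × 0.0625) = 0.486. R² = 0.352² / 0.486 = 0.25.

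**4. Standard error relative to always adjusting.** Never adjusting: 1/√(1 − R²). Adjusting only when a baseline test is significant: √(1 + K × R²/(1 − R²)), a large-sample form. K is the part of a standard normal's variance lying inside the non-significant region: 0.95 − 2 × 1.96 × 0.0584 = 0.721 for p < 0.05, and 0.80 − 2 × 1.2816 × 0.1755 = 0.350 for p < 0.20.

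| Correlation | ρ | R² | Never / always | p < 0.05 trigger / always | p < 0.20 trigger / always |
|---|---|---|---|---|---|
| Equal | 0.3 | 0.33 | 1.22 | 1.17 | 1.08 |
| Equal | 0.5 | 0.52 | 1.44 | 1.33 | 1.17 |
| Equal | 0.7 | 0.71 | 1.86 | 1.66 | 1.36 |
| Decay | 0.3 | 0.15 | 1.08 | 1.06 | 1.03 |
| Decay | 0.5 | 0.25 | 1.16 | 1.12 | 1.06 |
| Decay | 0.7 | 0.44 | 1.34 | 1.25 | 1.13 |

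Simulation at 48 per arm agrees to within about 0.02, with top values of 1.67 and 1.37 in the two trigger columns. The ratios are almost the same at 80 per arm. A p < 0.05 trigger fires in about 5% of randomised trials.

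**5. What imbalance can remain.** A baseline gap of up to 1.96 × √(2/48) = 0.40 SD escapes a 5% test at 48 per arm, or 1.96 × √(2/80) = 0.31 SD at 80. With an assumed utility SD of 0.25, equal correlation and ρ = 0.5, chance imbalance carries an SD of 0.5625 × 0.25 × √(2/48) = 0.029 QALY into the unadjusted difference. At 80 per arm it is 0.022, and 0.014 under decay.

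**6. Costs.** Assume four equal 3-month periods and equal correlation with baseline cost: R² = 4ρ²/(1 + 3ρ). Never against always adjusting is then 1.05 at ρ = 0.2, 1.11 at 0.3, 1.29 at 0.5 and 1.65 at 0.7. These too would fall if correlation decayed.

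**The case against.** Several points on the other side stand.

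- **No bias.** A reader might infer that the planned economic estimate is biased. Under randomisation it is not, averaged over trials. The matter is precision, imbalance in the trial at hand, and pre-specification.
- **Never adjusting is not the stated rule.** It is tempting to say that the plan carries 1.44 times the standard error it needs, or that power rises from 60% to 89% with adjustment. Those figures compare never with always adjusting, at an equal correlation of 0.5 borrowed from a depression score. With decay, the same comparison gives 1.16 and 60% to 73%.
- **No trigger is stated.** The text does not support saying that adjustment would normally be absent. It sets no test or threshold, and a looser trigger recovers much of the loss.
- **Decay is plausible.** The protocol describes an episodic illness, with patients symptomatic about half of the time (section 1) and median times to depressive relapse of 46 to 53 days in an earlier trial (section 7.2.2).
- **Costs differ from QALYs.** A large loss for costs cannot be inferred from the QALY figures. Conversely, the t-test and bootstrap test are stated for costs only, and the ICER formula could take adjusted differences.
- **Stratification helps somewhat.** Section 6.2 stratifies by site, gender, current or remitted depression, bipolar type and episode count. This should limit some imbalance in utility, though many strata weaken it.
- **An analysis plan may name the model.** The cited paper shows that the method is known to the authors.

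The last point does not remove the concern. The protocol does more than leave detail open: it states an affirmative look-then-decide rule, and no section overrides it.

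**Conclusion.** The concern holds as a point of pre-specification and precision in a secondary analysis. The conditional rule has no criterion, makes the estimator data-dependent, and cannot be expected to be more precise than always adjusting when baseline predicts the outcome.

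The size is not fixed by the documents. For QALYs, a conditional rule costs somewhere between about 3% and 67% in standard error, depending on the correlation, whether it decays, and the trigger. Never adjusting would cost 8% to 86%. For costs the gain is likely smaller: about 11% for never against always adjusting at an equal correlation of 0.3, and less if baseline cost predicts poorly. All of this rests on the trapezoid QALY and the assumed correlations. If the team would always have judged adjustment necessary, the change simply commits them to it.

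**What to change.** Replace the conditional sentence in section 8.2 with a fixed rule:

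- Incremental QALYs are estimated by regression on arm with baseline EQ-5D-5L utility as covariate, whatever the observed imbalance.
- Incremental costs are estimated by regression on arm with baseline TiC-P cost as covariate, likewise.
- Both regressions are refitted in every bootstrap replicate, so that the ICER, the plane and the acceptability curve use the adjusted differences.
- The baseline comparability analysis stays as description only and triggers nothing.

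The covariates should be measured before allocation. The text of section 6.3 says so, but Figure 2 lists randomisation ahead of T0, so the two should be aligned at the same time.

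The cost is a short change of wording and a regression in place of a difference in means. No extra data, visits or patients are needed.
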